5.4 Study Procedures During Treatment

Patients must meet eligibility criteria eligible on Day 1 and be enrolled prior to BRB treatment. BRB treatment should start within 14 days of enrollment.

Study Procedures, Cycle 1 Day 1 (refer to study calendar for specifics)

- Dispense BRB (Appendix 5)
- Concomitant medications
- Diet assessment (Appendix 6)
- Weight
- Adverse event assessment
- Physical exam
- Complete blood count (CBC) with differential and platelet count
- Study serum sample for anthocyanin level
- Study blood methylation samples
- Study urine samples
- Transfusion history

Study Procedures, Cycles 2-3, Day 1 (refer to study calendar for specifics)

These procedures must be completed cycles 2 - 3, day 1 (+/- 4 days).

- Dispense BRB (Appendix 5)
- Concomitant medications
- Diet assessment (Appendix 6)
- Adverse event assessment
- Complete blood count (CBC) with differential and platelet count
- Study blood methylation samples
- Transfusion history

Study Procedures, Cycles 4 & 7, Day 1 (refer to study calendar for specifics)

These procedures must be completed cycles 4 and 7, day 1. (+/- 4 days).

• Dispense BRB (Appendix 5)

- Concomitant medications
- Diet assessment (Appendix 6)
- ECOG performance status
- Weight
- Adverse event assessment
- Complete blood count (CBC) with differential and platelet count
- Serum chemistry panel, including: Alkaline phosphatase, aspartate aminotransferase/alanine aminotransferase (ALT/AST), total bilirubin, blood urea nitrogen (BUN), creatinine, total protein, albumin, potassium, sodium, chloride, bicarbonate, glucose
- Study blood methylation samples
- Disease response assessment (Appendix 2)
- Transfusion history

Study Procedures, Cycles 5-6 & 8-12, Day 1 (refer to study calendar for specifics)

These procedures must be completed cycles 5–6 and 8–12, day 1 (+/- 4 days).

- Dispense BRB (Appendix 5)
- Concomitant medications
- Diet assessment (Appendix 6)
- Weight
- Adverse event assessment
- Complete blood count (CBC) with differential and platelet count
- Study blood methylation samples (only cycle 10)
- Transfusion history

5.5 Follow-up

Perform follow-up procedures 30 days (+4 days) after study treatment discontinuation.

- Concomitant medications
- ECOG performance status
- Weight
- Adverse event assessment
- Physical exam
- Complete blood count (CBC) with differential and platelet count
- Serum chemistry panel, including: Alkaline phosphatase, aspartate aminotransferase/alanine aminotransferase (ALT/AST), total bilirubin, blood urea nitrogen (BUN), creatinine, total protein, albumin, potassium, sodium, chloride, bicarbonate, glucose
- Study blood methylation samples
- Disease response assessment
- Transfusion history

5.6 Study Withdrawal Procedures

Patients may continue treatment for one year from the time of study entry.

In the absence of treatment delays due to adverse events, treatment may continue until:

- Disease progression, as defined by the modified IWG criteria (Appendix 2)
- General or specific changes in the patient's condition render the patient unacceptable for further treatment in the investigator's judgment.
- Intercurrent illness that prevents further treatment administration
- Patient decides to withdraw from the study
- Significant patient noncompliance with protocol
- Unacceptable adverse event(s) per PI discretion

6 TREATMENT PLAN

6.1 Investigational Agent Administration

Treatment will be administered on an outpatient basis. MCW will obtain black raspberry powder directly from BerriProducts, Inc. in Corvallis, Oregon as study supply. Patients will be treated with 25 gm (2x/day) of BRB powder taken orally in 8 ounces of water. If the patient is tolerating and benefiting from treatment after three and six cycles, then, he or she will continue treatment for a total maximum of 12 cycles.

Study Drug	Dose	Route	Schedule	Cycle Length
Black Raspberries (Freeze-dried powder)	25 grams	Oral	Twice a day (each dose separated by at least 6 hours)	4 weeks (28 days)

6.2 Dosing Delays/Dose Modifications

Treatment or visit delays for public holidays or weather conditions do not constitute a protocol violation.

See the table below for dose modification requirements for nonhematological toxicities deemed clinically significant and related to BRB treatment by the treating physician.

Dose Modifications			
Dose Level	Dose of Study Drug		
0	25 grams twice a day with each dose separated by at least six hours (mixed in 8 ounces of water) ¹		
1	≥ grade 1 toxicity related to BRB treatment and unable to tolerate then dose reduce to 25 grams QD		
2	≥ grade 2 toxicity or grade 3 allergic reaction related to BRB treatment and/or unable to tolerate, withdraw patient from study		
Footnotes ¹	If unable to tolerate the taste, mix BRB with milk, ice cream or smoothie.		

Toxicity will be assessed according to the NCI Common Terminology Criteria for Adverse Events Version 4.0 (CTCAE v4.0).

6.3 General Concomitant Medication and Supportive Care Guidelines

The treating physician will use standard supportive care to control symptoms and improve quality of life. These may include:

- Transfusions
- Use of growth factors
- Antibiotics

6.4 Dietary Restrictions

There are no dietary restrictions. Patients will take BRB powder orally in 8 ounces of water. If the patient is unable to tolerate the taste of the BRB powder mixed in water, then, he or she may mix it with 8 ounces of milk, ice cream or a smoothie.

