6.6 Monitoring Subject Compliance

Black raspberries will be dispensed only to eligible patients under the supervision of the investigator or identified subinvestigator(s). The appropriate study personnel will maintain records of product receipt and dispensing. The patient will complete a drug diary to ensure compliance.

The patient will be seen every cycle by a healthcare professional or study staff for compliance. Patients will also be required to complete a food diary at home while taking BRBs and instructed to return the diary to clinic for assessment every cycle.

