Dispensing: Patients will receive oral black raspberries while receiving their supportive care. At office visits, patients will pick up black raspberry doses for the next cycle.

Compliance: Clinical staff will collect phenolic-rich food diaries from patients which reflect the previous cycle.

Handling

No special handling instructions.

Availability

The supplier is BerriProducts, Inc.

Agent Ordering

MCW will obtain black raspberry powder directly from BerriProducts, Inc. in Corvallis, Oregon as study supply.

Contact information: BerriProducts, Inc., [name]. [contact].

Agent Accountability

The investigator, or a responsible party designated by the investigator, must maintain a careful record of the inventory and disposition of black raspberries.

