9.2 Methods for Evaluation

All baseline evaluations will be performed as closely as possible to the beginning of treatment. Please refer to the study calendar and Section 3 (study design).

Physical Examination, Laboratory Values, Food Records

After completing a dietary assessment, patients will undergo physical examination and laboratory tests (complete blood count (CBC) with differential, platelet count, and serum chemistry assessment). The treating physician will evaluate the patient every cycle. Peripheral blood samples will be collected cycles 1–4, 7, 10, and EOT for evaluation of methylation status.

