9.3 Surrogate Endpoint Biomarkers

Plasma uptake and urine excretion of berry anthocyanins

We will evaluate the uptake of berry compounds into plasma obtained at two hours after the first dose of BRBs. Urine samples will also be collected three hours after the first dose of BRBs. The content of each of the four major anthocyanins in BRBs (i.e., cyanidin-3-rutinoside, cyanidin-3-sylosylrutinoside, cyanidin-3-glucoside and cyanidin-3-sambubioside) will be measured, using HPLC, as described previously. (17) Briefly, separation of plasma and urinary anthocyanins will be conducted on a Symmetry C18 column ($4.6 \times 75 \text{ mm}$, $3.5 \mu \text{m}$; Waters Corp.) using an HPLC system. Cyanidin-3-glucoside will be dissolved in deionized-distilled water containing 5% formic acid. All levels of anthocyanins analyzed in plasma and urine samples will fall within the standard curve range and will be expressed as cyanidin glucoside equivalents in pmol/mL plasma or urine.

DNA methylation analysis by reduced representation bisulfite sequencing (RRBS)

Peripheral blood will be used to isolate CD45+ leukocytes, using CD45 MicroBeads (Miltenyi Biotec). DNA will be extracted from isolated leukocytes (DNA extraction kit, Qiagen). Then, DNA samples will be used for RRBS analysis. In brief, first, genomic DNA is digested using a methylation-insensitive restriction enzyme. The next step is adding an extra adenosine to both the plus and minus strands. End repair and A-Tailing is done within the same reactions, with dCTP, dGTP and dATP deoxyribonucleotides. Then, methylated sequence adapters are ligated to the DNA fragments. The desired size of fragments is then selected to be purified. DNA fragments of 40-220 base pair are representative of the majority of promoter sequences and CpG islands. The DNA fragments are then bisulfite converted, which is a process that deaminates unmethylated cytosine into a uracil. The methylated cytosine remains unchanged, due to the methyl group protecting them from the reaction. The bisulfite converted DNA is then amplified, using PCR with primers that are complementary to the sequence adapters. The fragments are then sequenced. For Illumina sequencing, 36-base single-end sequencing reads are most commonly performed. Alignment to a reference genome allows the programs to identify base pairs within the genome that are methylated. The identified genes will be validated using pyrosequencing.

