APPENDIX 6. PHENOLIC-RICH FOOD DIARIES

Patient #: _____

Cycle #: _____

Dates Tracked:

Polyphenol Weekly Tracking

	Amount Consumed (in cups)						
Food Item	Monday	Tuesday	Wednesday	Thursday	Friday	Saturday	Sunday
Black chokeberry							
Dark chocolate							
Flaxseed meal							
Black elderberry							
Chestnut							
Lowbush blueberry							
Black currant							
Black olive							
Highbush blueberry							
Hazelnut							
Pecan nut							
Plum							
Green olive							
Sweet cherry							
Globe artichoke heads							
Blackberry							
Strawberry							
Red chicory							
Red raspberry							
Prune							
Black grape							

Patient Signature & Date: _____

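### No pre-BRB diet record is specified, and food and mixing vehicle are neither controlled nor logged between the Cycle 1 Day 1 anthocyanin samples; both gaps are cheap to close

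*Combined protocol and SAP*

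**What the plan says.** All references are to the combined protocol and SAP.

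- **Diet and vehicle.** Section 6.4: "There are no dietary restrictions". If the taste in water is not tolerated, "he or she may mix it with 8 ounces of milk, ice cream or a smoothie". What goes into the smoothie is not specified.
- **Diary period.** Section 6.6: "Patients will also be required to complete a food diary at home while taking BRBs". Section 8.1 (Nursing Implications): "Clinical staff will collect phenolic-rich food diaries from patients which reflect the previous cycle".
- **Diet assessment at Cycle 1 Day 1 (C1D1).** The study calendar and Section 5.4 list an Appendix 6 assessment on that day and at each later treatment visit, but not at screening. Section 9.2: "After completing a dietary assessment, patients will undergo physical examination and laboratory tests". None of these gives a recall period.
- **The form.** Appendix 6 is a Monday-to-Sunday tracker of 21 foods in cups, with blank fields for cycle number and dates. It has a row for "Red raspberry" and for other berries, but none for black raspberry.
- **Anthocyanins.** Blood is taken within 3 h before the first dose and at 2 h ± 30 min after it; urine within 3 h before and at 3 h ± 30 min after. Section 9.3 measures four named BRB anthocyanins individually by HPLC; levels "will be expressed as cyanidin glucoside equivalents in pmol/mL plasma or urine". Secondary objective 3 concerns blood only.
- **Analysis.** Section 10 summarises absolute and relative anthocyanin differences descriptively. It compares methylation at baseline with each treatment time in six mixed models with a random patient effect. Diet appears in neither.

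**The concern.** With no control arm, each patient's own baseline is the only comparator for methylation. The sponsor evidently regards phenolic-rich food as a background exposure worth following. If patients in a berry trial change how much fruit they eat, that change falls entirely after baseline, in the same direction in time as BRB. A diary that starts with treatment can describe diet on BRB but cannot show a change from before BRB. What is at stake is whether this rival explanation can be looked at when the results are read.

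The second issue is separate and smaller. The uptake endpoint rests on one pre/post pair per patient. Anthocyanin-containing food taken between the two samples, or blended with the dose, would be counted in the rise.

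**Working it through.** **1. Is a pre-BRB diet record specified?**

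| Place | What it fixes | Covers the days before BRB? |
|---|---|---|
| Section 6.6 | diary kept at home during BRB | no |
| Section 8.1 | diary covers the cycle just ended | there is none at C1D1 |
| Section 5.4, study calendar | Appendix 6 assessment at C1D1 | period not stated |
| Section 9.2 | dietary assessment precedes examination and tests | period not stated |
| Appendix 6 | one week, dates left blank | could, if told to |

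A C1D1 assessment completed before the first dose could capture pre-BRB diet, but no section tells staff or patients to use it that way. The places need reconciling.

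**2. The C1D1 interval.** Longest gap between samples = earliest pre-dose time + latest post-dose time.

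- Blood: 3 + 2.5 = 5.5 h
- Urine: 3 + 3.5 = 6.5 h

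Write the absolute difference as D = U + F − C, where U is the BRB contribution, F the contribution of other food taken between the samples or with the dose, and C the decline of whatever was present before. D measures uptake only if F and C are small. Habitual diet is largely in the pre-dose value, so it does not enter F. Food eaten before the pre-dose sample raises the denominator of the relative difference D/pre. The requisition form in Appendix 4 records collection and administration times but neither food nor vehicle. The Appendix 5 diary has dose times and a free comments column, with no vehicle field. Appendix 6 has daily amounts without clock times.

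**3. The plan's own sample size.** Inputs from Section 10: two-sided paired t-test, α = 0.05/24 = 0.00208, SD 8, difference 12. Exact power uses the noncentral t with n − 1 degrees of freedom and noncentrality (12/8)√n.

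- n = 15: power 0.9565
- n = 16: power 0.9735, so the stated 16 does suffice for 95%
- 16 × 1.05 × 1.05 = 17.64, rounded up to 18, as stated

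**4. What a diet shift would do, if there were one.** The smallest observed mean change that reaches significance is t × SD/√n.

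- n = 16: 3.713 × 8/√16 = 7.43
- n = 18: 3.627 × 8/√18 = 6.84

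Suppose BRB has no effect and a diet change moves the mean by b, in the units of the plan's power calculation. The value of b is an assumption. The chance that one comparison is declared significant is:

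| b | n = 16 | n = 18 |
|---|---|---|
| 0 | 0.2% | 0.2% |
| 2 | 1.3% | 1.6% |
| 4 | 8.5% | 10.8% |
| 6 | 29.6% | 37.1% |
| 8 | 61.6% | 71.6% |
| 12 | 97.4% | 99.1% |

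The table shows sensitivity only. It is not evidence that such a shift occurs.

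**The case against.** Confounding by a concurrent change is a general limit of any single-group pilot, the anthocyanin endpoint is secondary and descriptive, and nothing in the documents shows that diet moves leukocyte methylation. All of that is true, and it is why the point is an improvement and not a flaw that invalidates the trial. It does not remove the reason to collect the missing week, since the protocol already collects the rest.

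A reader might also infer more than the documents support:

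- **That no patient has a baseline diary.** An Appendix 6 assessment is listed at C1D1 and may have been completed for the preceding days. What is established is only that its period is undefined.
- **That the assay pools all anthocyanins and so cannot point to a source.** Section 9.3 measures each of four named compounds; the glucoside equivalent is the unit. The documents do not say whether these four are unique to black raspberry, so they neither establish nor exclude a contribution from other food.
- **That any breakfast would be reported as BRB uptake.** Breakfast may precede the pre-dose sample. The Background reports that no patient in the colon cancer study had detectable urinary BRB-derived anthocyanins before therapy, which eases concern about background levels, though it says nothing about food eaten between samples. The dose is also large: Section 8.1 puts roughly 500 berries in each 25 g packet. The smoothie is allowed only for taste intolerance and may be rare at a first dose.
- **That non-study black raspberry products must be banned.** No section suggests such use. A row to record it is enough.

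**Conclusion.** The point holds as a cheap improvement. The plan specifies no diet record for the period before BRB and uses the diaries in no analysis. As written, a post-baseline diet change therefore cannot be examined as an alternative to a BRB effect on methylation. Separately, food and vehicle are neither controlled nor logged over an interval of up to 5.5 h (blood) or 6.5 h (urine) around the C1D1 dose, so food taken then can add to the anthocyanin rise.

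The size of either bias is unknown. For methylation, a systematic shift of about 7 units would be needed before a single comparison reached significance about half the time without any BRB effect, taking the plan's SD of 8 and its Bonferroni level. Whether diet could produce such a shift is not stated anywhere. The documents support saying that the explanation cannot be checked. They do not support saying that the results will be biased.

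**What to change.** 1. **Reconcile Sections 5.4, 6.6 and 8.1.** Hand out the one-week Appendix 6 form at screening and collect it at C1D1 before the first dose. Show this in the study calendar.
2. **C1D1 sampling window only.** In Section 6.4 and Appendix 4, ask patients to avoid the berry and other dark-fruit items of Appendix 6 until the last post-dose sample. At minimum, record all food and the mixing vehicle on the requisition form. Show the uptake summary with and without affected pairs.
3. **Appendix 6.** Add a row for non-study black raspberry.
4. **Section 10.** Report the change in diary berry intake from the pre-BRB week, naming the on-treatment week it is compared with and how the rows are summed. Add a descriptive sensitivity analysis of the Cycle 4 Day 1 methylation contrast in patients with a pre-BRB diary.

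Section 10 reports seven patients already enrolled, so item 4 may cover only 18 − 7 = 11. With n = 11, the plan's own test at a difference of 12 has power 0.7626, which is a reason to keep this analysis descriptive.

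The cost is one form handed out at an existing visit, a short food request on one morning, a few added form fields and an incomplete baseline diary for patients already enrolled. The sample size and the primary analysis stay as they are.

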6.5 Prohibited Medications

As noted in the eligibility section 4, patients should not be receiving hypomethylating agents. In addition, they should not be receiving other chemotherapy/radiation, or participating in clinical trials with other investigational agents not included in this trial, within 14 days of the start of this trial and throughout the duration of this trial.

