Complete blood count (CBC) with differential and platelet count	x	x	x	x	x	x	x
Pregnancy test (serum or urine) ⁵	х						
Serum chemistry panel ⁶	Х			Х			Х
Research serum for anthocyanin level ^{7, 15}		х					
Research blood methylation samples ^{8, 15}		x	x	х	х		х
Research urine samples9, 15		х					
Disease Response Assessment ¹²				Х			х
Transfusion history ¹³		х	x	X	Х	Х	х

¹ Screening procedures should occur within 28 days prior to Day 1. BRB treatment should start within 14 days of enrollment.

 2 A follow-up visit is required 30 days (+/- 4 days) from treatment discontinuation.

³ BRBs will be dispensed every cycle for a maximum of 12 cycles. BRB doses should be separated by at least six hours and the morning dose should be held when the methylation research samples are collected. Refer to appendix 5 for the drug diary.

⁴ Capture medications taken within 30 days of day 1 of BRB treatment.

⁵ For women of childbearing potential. This is defined as any woman whether or not they have undergone tubal ligation, that meets the following: has not undergone a hysterectomy or bilateral oophorectomy or has not been naturally postmenopausal for at least one year.

⁶ Including albumin, total protein, total bilirubin, ALT, AST, alkaline phosphatase, bicarbonate, sodium, potassium, chloride, creatinine, BUN, and glucose.

- ⁷ Blood will be collected within three hours prior to BRB administration and at two hours (+/- 30 minutes) after first dose of BRBs.
- ⁸ Study blood methylation samples will be collected within three hours prior to BRB administration.
- ⁹ Urine will be collected within three hours prior to BRB administration and at three hours (+/- 30 minutes) after first dose of BRBs.
- ¹⁰ If the patient is tolerating BRBs well and is benefiting from therapy, he or she will continue treatment for a total maximum of 12 cycles.
- ¹¹ All adverse events will be followed with appropriate medical management from the date the patient takes their first BRB dose until 30 days following the last dose of treatment. AEs are monitored continuously from the first dose of treatment to 30 days' post last dose
- ¹² Benefiting from therapy (cycle 4 disease assessment) defined as CR, PR, HI, Stable disease with no disease progression (see appendix 2). Benefiting from therapy (cycle 7 disease assessment) defined as CR, PR, or HI (see appendix 2).)
- ¹³ Capture transfusion history from eight weeks prior to day 1 of BRB treatment.
- ¹⁴ Refer to appendix 6.
- ¹⁵ Refer to appendix 4.

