4.1 Inclusion Criteria

A potential subject must meet all the following inclusion criteria to be eligible to participate in the study.

1. Patients must have a confirmed diagnosis of myelodysplastic syndrome or myelodysplastic syndrome/ myeloproliferative neoplasms (MDS/MPN) proven by bone marrow biopsy/aspirate.

- 2. Patients with cytopenias (blood cell counts lower than the institutional lower limit of normal within the eight weeks prior to the study) who are receiving or received:
 - red blood cell transfusions
 - observation
 - platelet transfusions
 - erythropoietin
 - granulocyte colony-stimulating factors
 - granulocyte-macrophage colony-stimulating factors
 - hydrea
- 3. Age >18 years.
- 4. Predicted life expectancy of at least 12 weeks.
- 5. Patients should be expected to stay on the same therapy for the period of the study.
- 6. Patients who do not have an indication for and/or are believed to be unable to tolerate a hypomethylating agent are eligible for the study.
- 7. Reproductive requirements:

Female patients must meet one of the following:

- Postmenopausal for at least one year before the screening visit, or
- Surgically sterile, or
- If they are of childbearing potential, agree to practice two effective methods of contraception from the time of signing of the informed consent form through 30 days after the last dose of study drug, AND
- Must also adhere to the guidelines of any treatment-specific pregnancy prevention program, if applicable, or
- Agree to practice true abstinence when this is in line with the preferred and usual lifestyle of the subject. (Periodic abstinence [e.g., calendar, ovulation, symptothermal, postovulation methods] and withdrawal are not acceptable contraception methods.)

Male patients, even if surgically sterilized (i.e., status postvasectomy), must agree to one of the following:

- Practice effective barrier contraception during the entire study treatment period and through 30 days after the last study drug dose, OR
- Must also adhere to the guidelines of any treatment-specific pregnancy prevention program, if applicable, OR
- Agree to practice true abstinence when this is in line with the preferred and usual lifestyle of the subject. (Periodic abstinence [e.g., calendar, ovulation, symptothermal, postovulation methods] and withdrawal are not acceptable methods of contraception.)
- 8. Ability to understand a written informed consent document, and the willingness to signit.

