4.2 Exclusion Criteria

A potential subject who meets any of the following exclusion criteria is ineligible to participate in the study.

- 1. Previously received hypomethylating agents.
- 2. Allergy to black raspberries.
- 3. Inability to swallow oral medication.

- 4. Inability or unwillingness to comply with the BRB administration requirements.
- 5. Uncontrolled intercurrent illness, including, but not limited to, symptomatic congestive heart failure, or psychiatric illness/social situations, that, in the treating investigator's discretion, would limit compliance with study requirements. Concurrent active malignancy is not an exclusion criterion.
- 6. Active infection not well controlled by antibacterial or antiviral therapy.
- 7. Pregnant or lactating women.
- 8. Participation in clinical trials with other investigational agents not included in this trial, within 14 days of the start of this trial and throughout the duration of this trial.
- 9. Patients with allergies to other members of the Rosacea family, including but not limited to apple, almond, apricot, cloudberry, blackberry, etc.

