APPENDIX 2. MODIFIED IWG RESPONSE CRITERIA

Hematologic	Response Criteria (responses must last at least 8 weeks)				
Improvement (HI)					
Erythroid response	- Hgb increase by ≥ 1.5 g/dL.				
(pretreatment, < 11 a/dL)	- Relevant reduction of RBC transfusion units by an absolute				
. ,	number of at least 4 RBC transfusions/8 wk compared with				
	the pretreatment transfusion number in the previous 8 wk.				
	- Only RBC transfusions given for an Hgb of \leq 9.0 g/dL				
	pretreatment will count in the RBC transfusion response				
	evaluation.				
Platelet response	- Absolute increase of \geq 30 x 109/L for patients starting with				
(pretreatment, < 100 x 109/L)	> 20 x 109/L platelet.				
	- Increase from < 20 x 109/L to > 20 x 109/L and by at least				
	100%.				
Neutrophil	At least 100% increase and an absolute increase > 0.5 x 109/L.				
response (pretreatment					
< 1.0 x 109/L)					
Progression or	At least one of the following:				
relapse after HI	- At least 50% decrement from maximum response levels in				
	aranulocytes or platelets				
	= Reduction in Hab by > 1.5 a/dl				
	- Reduction in rigb by ≥ 1.5 g/dE.				
	- i ransiusion dependence in transfusion independent				
	patients.				

Category	Response criteria (responses must last at least 4 weeks)
Complete remission	Bone marrow: ≤ 5% myeloblasts with normal maturation of all cell lines Persistent dysplasia will be noted
	Peripheral blood: Hgb \geq 11 g/dL Platelets \geq 100 × 10 ⁹ /L Neutrophils \geq 1.0 × 10 ⁹ /L Blasts 0%
Partial remission	All CR criteria if abnormal before treatment except: Bone marrow blasts decreased by ≥ 50% over pretreatment but still > 5% Cellularity and morphology not relevant
Marrow CR	Bone marrow: $\leq 5\%$ myeloblasts and decrease by $\geq 50\%$ over pretreatment
	Peripheral blood: if HI responses, they will be noted in addition to marrow CR
Stable disease	Failure to achieve at least PR, but no evidence of progression for > 8 weeks.
Failure	Death during treatment or disease progression characterized by worsening of cytopenias, increase in percentage of bone marrow blasts, or progression to a more advanced MDS FAB subtype than pretreatment
Cytogenetic response	Complete: Disappearance of the chromosomal abnormality without appearance of new ones Partial: At least 50% reduction of the chromosomal abnormality

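### The 14-day chemotherapy/radiation window in Section 6.5 is shorter than the 8-week transfusion baseline in Appendix 2, so a compliant patient can be scored HI-erythroid because chemotherapy-related transfusions stopped

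*Combined protocol and SAP*

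**What the plan says.** Section 6.5 states that "they should not be receiving other chemotherapy/radiation, or participating in clinical trials with other investigational agents not included in this trial, within 14 days". The 14 days are counted from the trial's start, and the same things are barred while the trial runs.

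The erythroid part of hematologic improvement (HI) in Appendix 2 applies to patients with pretreatment Hgb below 11 g/dL. One of its criteria is a fall in RBC units by an absolute "number of at least 4 RBC transfusions/8 wk compared with" a baseline, and Appendix 2 takes as that baseline "the pretreatment transfusion number in the previous 8 wk". Units count only if given for Hgb ≤ 9.0 g/dL, and HI must last at least 8 weeks.

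The Study Calendar collects data to match: "Capture transfusion history from eight weeks prior to day 1 of BRB treatment" (footnote 13). For drugs the look-back is shorter: "Capture medications taken within 30 days of day 1 of BRB treatment" (footnote 4). Footnote 1 adds that "BRB treatment should start within 14 days of enrollment".

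On eligibility, inclusion 2 in Section 4.1 accepts "blood cell counts lower than the institutional lower limit of normal within the eight weeks prior to the study". Exclusion 5 in Section 4.2 adds: "Concurrent active malignancy is not an exclusion criterion". Section 4.2 excludes earlier hypomethylating agents but no other earlier chemotherapy.

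Best response by Appendix 2 is a secondary endpoint (Section 3.4). Under Section 3.1, stable disease is enough to continue at the first assessment (C4D1). The second (C7D1) requires CR, PR or HI.

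**The concern.** The baseline for a before/after comparison should describe the patient's transfusion need under the conditions that also hold on study. Here the comparison period bars chemotherapy and radiation, but most of the baseline period need not be free of them. A patient transfused during treatment for another cancer would carry those units into the pretreatment count. If the need ends with that treatment, the fall is credited to BRB.

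The study has one group, so no control arm shows how often this happens without BRB. The same score also opens cycles 7 to 12, so it affects treatment as well as reporting.

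**Working it through.** The plan gives no figure for this point, so there is none to reproduce. The check is window arithmetic, a search for a rule that closes the gap, and an illustration.

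**1. Exposed share of the baseline.** The baseline is 8 × 7 = 56 days (Appendix 2; footnote 13).
- Start = C1D1: 14 clean days. 56 − 14 = 42 days (−56 to −15); 42/56 = 75%.
- Start = enrolment, with the full 14-day delay (footnote 1): 14 + 14 = 28 clean days. 56 − 28 = 28; 28/56 = 50%.
- If the 14 days in 6.5 attach only to other investigational trials, chemotherapy has no stated washout and the share could be larger.

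**2. Worked case.** The patient has a concurrent malignancy, treatment ending on day −15, and pretreatment Hgb below 11 g/dL. Suppose 4 units at Hgb ≤ 9.0 g/dL on days −56 to −15 and none in 8 weeks on study. The fall is 4 − 0 = 4 units per 8 weeks, which meets the rule. C4D1 is day 1 + 3 × 28 = 85, so 8 weeks fit before the first assessment. C7D1 is day 1 + 6 × 28 = 169, and passing it opens 12 − 6 = 6 more cycles.

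**3. Does another rule close the gap?**
- Inclusion 5 asks for stable therapy over the study period. It looks forward, not over the previous 8 weeks.
- The Hgb ≤ 9.0 filter says nothing about why a unit was needed.
- The 8-week duration rule does not help, because chemotherapy stays barred and the fall can persist.
- Sections 9 and 10 have no rule that resets or sets aside such a baseline.
- The 30-day medication history leaves 56 − 30 = 26 days (46%) outside that record.

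**4. Illustration, given that such a patient exists.** Assume Poisson transfusions: *c* units/week while exposed, *b* units/week otherwise, no BRB effect, and need returning to *b* the day therapy ends. With *w* clean days, the baseline mean is c(56 − w)/7 + b·w/7 and the on-study mean is 8b. The chance that baseline minus on-study units is at least 4 is:

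| b | c | w = 14 | w = 28 | no exposure |
|---|---|---|---|---|
| 0 | 0.5 | 35.3% | 14.3% | 0% |
| 0 | 1.0 | 84.9% | 56.7% | 0% |
| 0.25 | 0.5 | 19.0% | 12.8% | 3.9% |
| 0.25 | 1.0 | 62.5% | 41.3% | 3.9% |
| 0.5 | 1.0 | 43.4% | 31.2% | 10.5% |

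All rates are assumptions; the documents give none.

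**5. Effect on the reported rate.** Assume 0 to 2 affected patients and all 18 evaluable (Section 9.1 requires three cycles, so the denominator may be smaller). Exact 95% intervals: 0/18 = 0% (upper limit 18.5%); 1/18 = 5.6% (0.1% to 27.3%); 2/18 = 11.1% (1.4% to 34.7%).

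**The case against.** The scenario needs several things at once: MDS or MDS/MPN, a second treated cancer, treatment ending between days −56 and −15, at least 4 qualifying units, and then a sustained fall although the MDS persists. Inclusion 2 describes a supportive-care population. Inclusion 5 and Section 6.5 together imply a patient not expected to need more chemotherapy. Response is secondary, and Section 10 sets no test or threshold for it. At C4 stable disease already permits continuing. The extra exposure is to a powder from which the protocol summary expects no toxicity. All of this stands and limits the weight of the point. It does not close the gap, because exclusion 5 expressly lets these patients in.

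Four stronger readings are tempting, and the documents do not support them.
- *The error always favours BRB.* This is not shown. Suppression lasting past day 1 would raise on-study transfusions and could mask a response.
- *The response rate will be inflated.* The documents give no count of such patients, and zero is possible.
- *The exposure would go unrecorded.* Section 5.3 requires a medical history with no stated look-back limit, which may well show it. What is missing is an instruction to use it in scoring.
- *A 56-day washout would cure the problem.* Therapy ending on day −57 can still cause transfusions that count from day −56.

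One ambiguity remains. Appendix 2 lists the Hgb rise and the transfusion reduction without a connecting word. I read them as alternatives, as the two platelet criteria must be, since they apply to different starting counts. If both were required, the route would be narrower, though marrow recovery could also raise Hgb.

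**Conclusion.** The gap is real but limited. Followed as written, Section 6.5 and Appendix 2 let 42 of 56 baseline days (28 on the enrolment reading) fall under chemotherapy or radiation. A compliant patient can then meet the HI-erythroid transfusion rule because related transfusions ended.

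Each such patient would add 1/18 = 5.6 percentage points to the response rate if all 18 are evaluable, and could receive up to six further cycles on that score. This rests on reading the erythroid criteria as alternatives and on at least one such patient enrolling, which the documents neither show nor rule out. The direction of the net error is not established.

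A reader might infer that the methylation result is affected too. It is not affected by this route, because that analysis does not use the transfusion baseline. The point deserves a correction because the correction is cheap, not because the trial's main conclusion is at risk.

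**What to change.** Keep 14 days as the entry window and make two small changes by IRB-approved amendment.

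1. **Appendix 2, one line.** If chemotherapy (other than hydrea permitted by inclusion 2) or radiation was given on days −56 to −1, the transfusion-reduction component of HI-erythroid is not evaluable and is not by itself grounds for continuing at C7. CR, PR and the other HI components are scored as usual.
2. **Study Calendar footnote 4.** Extend the look-back to 8 weeks for these therapies. For patients already enrolled (Section 10 mentions seven), check the medical history instead. Apply the rule on exposure alone, whatever the patient's response, and report how many patients it affects.

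The cost is one line, one number and a records check, with no new visits or samples. An affected patient loses one HI component. Transfusions caused by therapy that ended just before day −56 are still counted, so the bias is reduced rather than removed.

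Lengthening the entry window to 56 days is the alternative. It could delay candidates by up to 56 − 14 = 42 days and leaves the same residual problem, so I would not prefer it.
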